### **Research Procedures**

A reference notch will be made on the temporary crown with #1/2 bur at a 2 mm distance from the gingival margin at the mesiobuccal, midbuccal and distobuccal sites. The following measurements will be carried out:

1)Soft tissue distance from each of the three notches (mesiobuccally, midbuccally and distobuccally, respectively) at implant placement visit, following suturing, 4weeks, 6 weeks, 8 weeks, 3 months and 6 months. At 12-18 months these measurements will be performed using acrylic stent recoding previous reference points.

2a) Horizontal defect dimension (HDD) defined as horizontal distance from the implant shoulder to the alveolar socket wall, measured in 3 sites: mesial, buccal and distal; measured only at implant placement visit.

2b) Vertical defect dimension (VDD) defined as vertical distance from implant shoulder to the apical contact with the socket wall, measured in 3 sites: mesial, buccal and distal; measured only at implant placement visit.

2c) Buccal soft tissue and buccal plate thickness will be measured following the extraction using digital calipers (one measurement/ midbuccal/6mm apical to gingival margin); measured at implant placement only.

2d) Pocket depth (PD): pocket depth is defined as the distance from the gingival margin to the tip point of the probe (Williams probe). PDs will be measured at 6 sites per tooth, (mesiobuccal, midbuccal, distobuccal, distopalatal, midpalatal, mesiopalatal); measured before surgery and at 6months and 12-18 months.

2e) Buccal dimension of the ridge at the site of implant placement: measured after implant placement during surgery, at 3 months, 6 months and at 12-18 months.

2f) Impressions for study models will be taken first visit, following implant placement and temporization (on the day of surgery), at 8 weeks, 6 months and 12-18 months.

3) Interproximal bone level: a film holder with silicon putty to aid in reproducibility of the radiograph position will be used. The mesial and distal crestal bone level will be measured using the MIPACS software. Implant platform will serve as the reference point. Vertical and horizontal changes (depth and width of the vertical defect on the mesial and/ or distal aspect of the implant, if present) will be measured from radiographs taken at the time of completion of surgery, at 6 months and 12-18 months. Dose and frequency of x-rays in the study are standard of care for any implant patient in CDM or in standard clinical practice, and are not altered for the purpose of the study. (Medical status is updated and recorded at each CDM visit, including verification that female patients are not pregnant prior to x-ray taking; this is also standard of care).

4) The diameter of the apical radiolucency, when initially present, will be monitored /radiographically at will be assessed immediately after surgery at 6 months and at 12-18 months.

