**Research question(s):**

1. Primary goal is to study the effect of the surgical technique (flap elevation or flapless) on the change in soft tissue (papillary height and facial margin level) between pre-operative level and up to 12-18 months following immediate implant placement and crown temporization.
2. Second goal is to study the effects of surgical technique (flap or flapless) and horizontal/vertical extraction socket dimensions on the lateral ridge dimensions and interproximal bone level adjacent to the implant 12-18 months following surgery.

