**Scientific abstract:**

Immediate implant placement following tooth extraction has become a predictable method of therapy. Advantage of this method combined with immediate temporization, is evident in the maxillary esthetic zone, since it allows most continuous support of soft tissue contour. Surgical implant placement can be accomplished following elevation of a soft tissue flap or with a flapless approach. Numerous studies have demonstrated alveolar ridge remodeling with net bone loss at 6 months following elevation of flap (Schropp and Isidor, 2008, Buser et al., 2011). It is not clear, how this finding affects clinical changes in ridge dimensions (soft and hard tissue). Several uncontrolled trials have reported outcomes using the flapless technique (Raes et al., 2011, Van de Velde et al., 2010, Block et al., 2009), but no randomized controlled studies comparing these two methods are available. The aim of this study is to compare 1) the remodeling of the gingival tissue margin (change in papillary distance, gingival margin level / recession), and 2) the dimensional changes of the ridge and the stability of the radiographic alveolar bone level following immediate implant placement, temporization and restoration with or without flap elevation.

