### **Study Design and Statistical Procedures Overview**

We propose to conduct a randomized controlled trial with two treatment arms: one in which immediate implant placement after tooth extraction is carried out after conventional mucoperiosteal flap elevation, and another that will adopt a flapless approach. Only maxillary teeth in the esthetic zone will be included. The primary outcome of the study is the gingival margin alterations at 12-18 months after surgery while the secondary outcome is the dimensional changes of the ridge at 12-18 months.

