### **Study Procedures**

After informed consent is obtained, and initial periodontal therapy, whenever indicated, the scheduled extraction will be carried out without flap elevation, and the socket will be debrided meticulously. After verification that the local anatomical inclusion criteria are met, patients will be randomized to one of two treatment groups, a test (flapless group) and a control group (flap group). In the test group, the implant will be placed according to standard protocol at a position engaging the palatal wall without elevation of a mucoperiosteal flap. In the control group, intrasulcular incisions will be carried out from one tooth distal to one tooth mesial to the extraction site and full thickness flaps will be elevated with periosteal elevator, including the papillae. The implant will be placed according to standard protocol at a position engaging the palatal wall, and the flaps will be sutured using a combination of interrupted and mattress sutures.

In both groups, temporary restorations will be delivered immediately after implant placement provided that the implant shows primary stability and has engaged in the bone with an insertion torque of 25Ncm or more (Norton, 2004). In case of a lower insertion torque, the protocol will be abandoned, a cover screw will be placed, and a two stage implant protocol will be followed. All patients will be advised to receive a permanent restoration 6 months after surgery, if the implant is deemed to be successful (Misch et al., 2008).

All patients will receive antibiotics 1 hour prior to surgery (Amoxicillin 1g; in allergic patients Clindamycin 300mg) and will continue with Amoxicillin 500mg (Clindamycin 150 mg) tid for seven days following surgery. All patients will be seen 1 week following surgery (suture removal visit, if applicable), review of OH; at two weeks following surgery, follow up of healing and OH; at 4 weeks, 6 weeks and 8 weeks (prophylaxis and measurements); at 3 months (prophylaxis and measurements); at 6 months (prophylaxis, measurements; removal of temporary restorations and impressions for permanent prosthesis, which will be delivered subsequently, can be done by restorative dentist or student at this visit or later) and at 12-18 months (prophylaxis, measurements).

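### Papillary height is part of the primary aim, but no planned reading is defined as papillary height, and the crown-notch readings cannot give its change from the pre-operative level

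*Combined protocol and SAP*

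**What the plan says.** Research question(s), item 1, sets the primary goal as the effect of surgical technique on the "change in soft tissue (papillary height and facial margin level) between pre-operative level and up to 12-18 months" after surgery. The Scientific abstract describes the same aim as "change in papillary distance, gingival margin level / recession". The Study Design and Statistical Procedures Overview does not mention the papilla: "The primary outcome of the study is the gingival margin alterations at 12-18 months after surgery".

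Research Procedures places reference notches on the temporary crown "at a 2 mm distance from the gingival margin at the mesiobuccal, midbuccal and distobuccal sites". Item 1 then records "Soft tissue distance from each of the three notches (mesiobuccally, midbuccally and distobuccally, respectively") at the implant placement visit after suturing, at 4, 6 and 8 weeks, and at 3 and 6 months. At 12-18 months an acrylic stent carries the reference points forward. Item 2f schedules impressions for study models at the first visit, on the day of surgery, at 8 weeks, at 6 months and at 12-18 months, but specifies no reading from them.

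**The concern.** A primary aim with two components needs a measurement rule for each. For the papilla, the plan gives no landmark, no reference point, no data source and no rule for combining the mesial and distal values. Two examiners could both follow item 1 and record different things at the mesiobuccal and distobuccal sites, one reading to the margin of the crown and the other to the tip of the papilla.

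The baseline is a separate problem. The aim is change from the pre-operative level, yet the first notch reading comes after the implant, the temporary crown and any sutures are in place. In the control arm, "full thickness flaps will be elevated with periosteal elevator, including the papillae" before that reading; in the test arm no flap is raised. Any shift in papillary level between the pre-operative state and the end of surgery is therefore outside the notch data, and the two arms are treated differently over just that interval.

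**Working it through.** The point concerns how an outcome is defined, so most of the check sets sections side by side.

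**1. Is the papilla part of the primary aim?** Research question(s) says yes, as does the closing statement of the soft-tissue rationale in Study Purpose and Rationale. The Scientific abstract lists papillary distance beside margin level or recession. The design overview names gingival margin alterations only. The sections are not aligned.

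**2. Which planned items could yield papillary height?**

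| Item in Research Procedures | Taken before surgery? | Tied to the papilla? |
|---|---|---|
| 1, notch distances | No, the crown does not yet exist | Not stated; soft-tissue end point undefined |
| 2a-2c, defect dimensions and buccal thickness | No | No |
| 2d, pocket depth | Yes | No; measured from the gingival margin to the probe tip, so it has no fixed level reference |
| 2e, buccal ridge dimension | No | No |
| 2f, study models | Yes, first visit | Not stated; no reading specified |
| 3-4, radiographs | No, from completion of surgery | No; bone level and apical lesion |

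No item names the papilla. Only the first-visit study model could carry a pre-operative papillary level.

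**3. Do the site names settle the notch end point?** Item 2d uses the same labels: "PDs will be measured at 6 sites per tooth, (mesiobuccal, midbuccal, distobuccal, distopalatal, midpalatal, mesiopalatal"). There they are positions around a tooth. This suggests that the notch sites are also marginal positions, but a label for position does not say which soft-tissue point is read there.

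**4. Does the sample size show which component was meant?** Power Calculations and Statistical Analysis gives 17 per group, 80% power and a 0.5 mm difference in soft-tissue change, without an SD or an alpha. Assume two-sided alpha 0.05:

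n per group = 2 × (1.96 + 0.8416)² × SD² / 0.5²

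- SD 0.50 (assumed): 2 × 7.849 × 0.2500 / 0.25 = 15.7, so 16; the t-based calculation gives 17, the stated figure.
- SD 0.53 (midbuccal, from the 35-implant case series in Study Purpose and Rationale): 2 × 7.849 × 0.2809 / 0.25 = 17.6, so 18; t-based 19.
- SD 0.39 (interproximal, same series): 2 × 7.849 × 0.1521 / 0.25 = 9.6, so 10; t-based 11.

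The stated 17 implies an SD of about 0.50 (t) to 0.52 (normal). That is close to the midbuccal value and not to the interproximal one. It is consistent with sizing on the facial margin, but with no SD stated it proves nothing. If papillary change did have an SD of 0.39, 17 per group would give about 95% power for 0.5 mm. The gap is therefore one of definition and baseline; this calculation does not show a shortage of patients for the papilla.

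**5. Cost of the remedy.** 2 papillae × 5 scheduled models × 40 patients = 400 readings at most.

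**The case against.** The best defence is that the mapping is implicit. The abstract places papillary distance within remodelling of the gingival tissue margin, so the primary outcome in the design overview may be meant to cover it. Three notches fit two components naturally: mesiobuccal and distobuccal for the papillae, midbuccal for the facial margin. The text fixes only where each notch is cut, so the distance may well run to the papilla tip. The study models also mean that no source data are missing.

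Much of this stands. A reader might infer that none of the notch readings is at the papilla tip, so that papillary change cannot come from the planned data. The documents do not support that: the end point is undefined, and the models could supply the measure. A reader might go further and expect the papillary comparison to be biased toward no difference because a margin reading catches only part of the change at the tip. Nothing in the documents gives such a capture fraction, and the bias would depend on an end point that is not stated. The cited interproximal change of -0.53 mm or less is a within-group change in an uncontrolled series; it does not estimate the difference between flap and flapless surgery.

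What the defence does not answer is the baseline. Even with the implicit mapping accepted, notches on a crown made at surgery cannot measure change from before surgery. An adjacent-tooth landmark is not the only possible definition, but it is one that works on a pre-operative model as well as on later ones.

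**Conclusion.** The point holds as a gap in definition and baseline. One of the two soft-tissue components of the primary aim has no reading defined for it, and the only level readings that might serve start after the randomized procedure. The sections also disagree, or at least are unclear, on whether papillary change is part of the primary outcome. No effect on the estimated treatment difference can be quantified from the documents, and neither a direction nor a size of bias is claimed. The conclusion assumes that the removed or unreadable parts of the document contain no papillary definition. The proposed baseline assumes that the first-visit model is taken before the extraction, which the schedule implies but does not state. It should be corrected before the models are read and the primary outcome is analysed.

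**What to change.** - Define papillary height as the vertical distance from the mesial and the distal papilla tip to a fixed landmark on the adjacent natural tooth. Inclusion Criteria require both adjacent teeth to be present.
- Read it on the study models already scheduled at the first visit, on the day of surgery, at 8 weeks, at 6 months and at 12-18 months. Use the first-visit model as the pre-operative baseline, and confirm that it precedes the extraction.
- State how the mesial and distal values are combined or reported.
- State the soft-tissue end point of the mesiobuccal and distobuccal notch readings, and call them papillary height only if that end point is the papilla tip. Otherwise report them as marginal level.
- Reconcile Research question(s), the Scientific abstract, the design overview and Research Procedures on whether papillary change is part of the primary outcome.

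The cost is two extra readings per model, up to about 400 in 40 patients, with the reader time and training that this takes. No visit or impression is added.

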Immediate implant placement does not preclude vertical and horizontal alveolar ridge loss following the extraction. In a study of hard tissue changes following immediate implant placement in 21 human extraction sites, significant postsurgical dimensional alterations were noted at 4 months following implant surgery (horizontal resorption amounting to 56% of the buccal bone and 30 % of the lingual bone), in spite of predictable new bone formation at the inner side of the extraction socket (Botticelli et al., 2004). Mucoperiosteal flaps were elevated in this study prior to extraction and implant placement. Elevation of full thickness flap induces accelerated bone remodeling of alveolar bone and net bone loss in the range of 0.5-1.0mm between 3 and 6 months following surgery (Donnenfeld et al., 1964, Wood et al., 1972, Pennel et al., 1967, Moghaddas and Stahl, 1980, Gomez-Roman, 2001). The question then arises, whether flapless immediate implantation will result in diminished horizontal bone loss, entailing enhanced ridge stability during the first 6 months following surgery. Therefore, the second aim of our study is to investigate the impact of surgical technique and extraction socket dimensions on the changes of the lateral ridge dimension and the interproximal bone level adjacent to the implant up to 12-18 months following surgery.

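### The ridge baseline is taken during surgery, when only one arm has had a flap raised, and its tissue state is not fixed; if it is read with the flap open, ridge change is biased between arms

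*Combined protocol and SAP*

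**What the plan says.** Study Design and Statistical Procedures Overview gives ridge change a named role: "the secondary outcome is the dimensional changes of the ridge at 12-18 months". The measurement is item 2e of Research Procedures. It is identified only as "Buccal dimension of the ridge at the site of implant placement" and is "measured after implant placement during surgery, at 3 months, 6 months and at 12-18 months". No landmark, level, tissue or instrument is attached to it.

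Study Procedures sets the order of the operation. Extraction is flapless for everyone, the socket anatomy is checked, and the patient is then randomised. In the control arm "full thickness flaps will be elevated with periosteal elevator, including the papillae"; the implant is placed, and the flaps are then sutured. In the test arm the implant is placed with the mucosa undisturbed.

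Other measurements are timed differently. Item 1 (soft tissue) is taken "at implant placement visit, following suturing". The item 3 radiographs are timed to when surgery is complete. Item 2f takes study models at the first visit, on the day of surgery after temporization, at 8 weeks, at 6 months and at 12-18 months. Item 2c records buccal soft tissue and buccal plate thickness once, after extraction.

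**The concern.** A change score compares arms fairly only if baseline and follow-up measure the same thing in both. Item 2e takes its baseline at the one point where the arms differ by design in whether the facial mucosa is in place. No re-entry surgery is described, so later readings must be over mucosa in both arms.

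If the control-arm baseline is on exposed bone, its change score contains the mucosal thickness as an apparent gain, and the flapless arm's does not. The offset belongs to the treatment difference itself. Randomisation cannot balance it, and a larger sample only makes it easier to declare significant. It runs against the trial's own hypothesis, because it makes flap surgery look kinder to the ridge. It could hide or reverse the benefit that Study Purpose and Rationale asks about.

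**Working it through.** **The plan's own figure.** Power Calculations and Statistical Analysis gives 17 per group for 80% power to detect 0.5 mm in soft tissue change. It states no SD or alpha. With two-sided alpha 0.05 assumed, n = 2(1.960 + 0.842)² SD²/0.5².
- SD 0.50 mm: 15.7, so 16 (17 by the t-test version).
- SD 0.53 mm (the midbuccal soft tissue SD in Study Purpose and Rationale): 17.6, so 18 (19 by the t-test version).

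The stated 17 is therefore consistent with an SD near 0.5 mm. It concerns soft tissue, not the ridge. Only the sample size is carried forward.

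**Timing, side by side.**
- Item 1 says after suturing.
- Item 3 says at the end of surgery.
- Item 2f says after temporization.
- Item 2e says after implant placement and during surgery.

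In the control arm implant placement comes before suturing, so item 2e can fall on either side of closure. The contrast with the other items makes the open-flap interval the more natural reading, but the text does not settle it.

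**Bias if the flap is open.** Let b be the mucosal thickness missing from the control baseline.
- Flapless arm: observed loss = true loss.
- Flap arm: observed loss = true loss − b.
- Observed extra loss with a flap = true extra loss − b.

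The rationale cites "net bone loss in the range of 0.5-1.0mm between 3 and 6 months following surgery" after full-thickness flaps. Taking 0.5 and 1.0 mm as illustrative true differences:

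| True extra flap loss | b = 0.5 mm | b = 1.0 mm |
|---|---|---|
| 0.5 mm | 0.0 | −0.5 (reversed) |
| 1.0 mm | 0.5 | 0.0 |

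**False significance with no true difference.** Two-sample t-test, 17 per arm, 32 degrees of freedom, critical value 2.037, noncentrality (b/SD)√(17/2). The documents give neither b nor an SD for ridge change, so both are assumed. The 0.53 mm row borrows the soft tissue SD.

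| SD of change | b = 0.25 mm | b = 0.5 mm | b = 1.0 mm |
|---|---|---|---|
| 0.53 mm | 27% | 76% | about 100% |
| 0.75 mm | 16% | 47% | 97% (96.5%) |
| 1.0 mm | 11% | 29% | 81% |

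For example, at SD 0.75 and b = 0.5 the noncentrality is 0.667 × 2.915 = 1.94, which gives 47%. With a common baseline b = 0 and the rate returns to 5%.

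**If the reading follows closure.** Mucosa is present in both arms, and b no longer applies. A freshly sutured flap is still compared with undisturbed mucosa. The documents give nothing from which to size that difference.

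**The case against.** A reader might infer that the control baseline is bone-only and that the secondary outcome is therefore biased. The documents do not support that as a statement of fact. Suturing is part of surgery and follows implant placement, so a reading after closure also satisfies item 2e. The Scientific abstract describes ridge dimensions as both soft and hard tissue, which points towards measuring over mucosa throughout. Item 1 has its own reason to wait for suturing, since a gingival margin cannot be measured with the flap reflected. The analysis section does not name the intra-operative value as the baseline either. All of this stands, and it makes the main finding conditional.

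A reader might also infer that the artefact must equal or exceed the effect sought. It need not: a 0.5 mm offset is smaller than a 1.0 mm effect. Nor is the cited 0.5-1.0 mm presented as a horizontal, between-arm or 12-18-month difference.

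Item 2c might help to size an open-flap offset. It is a single midbuccal reading 6 mm apical to the gingival margin, with no stated link to the level used in item 2e, and no adjustment using it is planned. It is not a dependable correction.

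The objections do not remove the core problem. Staff who follow item 2e to the letter could measure different tissue in the two arms, and nothing in the plan prevents it.

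**Conclusion.** The point holds as a conditional one. The baseline is scheduled when the arms already differ in flap status, and timing relative to closure, tissue, level and landmark are left open. With an open flap, flap-arm loss is understated by the mucosal thickness. The error rates shown then apply, subject to the assumed offset and SD, alpha 0.05 and 17 analysed per arm. With a closed flap, the bias is smaller and cannot be quantified from the documents.

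The effect is confined to the clinical ridge measurement. The primary gingival-margin outcome is not touched, and neither is the radiographic interproximal bone level, which is referenced to the implant platform. This should be fixed, because the outcome is a named one and the remedy is cheap, but it does not undermine the trial's main comparison.

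**What to change.** Rewrite item 2e to define the level and landmark relative to the adjacent teeth, and name a change-score baseline in the same tissue state in both arms. Two options are available.

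1. **Direct reading over mucosa, after extraction and before any incision.** Extraction is flapless in both arms and precedes randomisation, so the reading can be taken before allocation. It keeps the 3-month comparison. It must be in place before patients are treated, because a missed reading cannot be recovered.
2. **First-visit study model**, compared with the 6-month and 12-18-month models already collected under item 2f. This needs only caliper readings on existing models. There is no 3-month model, and the baseline model includes the tooth and may precede initial periodontal therapy. Both limitations apply equally to the two arms.

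The same-day model after temporization is less suitable, since it records a freshly sutured flap in one arm only.

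Under either option the intra-operative reading is kept as descriptive and is not used in the change score. The cost is a protocol wording change, one extra reading or some model measurements, and the demotion of the intra-operative value. The sample size does not change.

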### **Study Subjects**

Forty subjects will be recruited among the patients attending the Clinic for Graduate Periodontics, College of Dental Medicine, Columbia University, who are in need of a tooth extraction at the maxillary premolar, canine and incisor region, and subsequent single implant placement. The reasons for extraction will include poor endodontic prognosis and/or non-restorable teeth (extensive caries, traumatic fractures, fractures of endodontically treated teeth, root perforation, root resorption, with or without radiographic periapical lesion up to 5 mm in diameter).

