### **Potential Risks**

- 1) Study related risks: Initial infection, pain or esthetically adverse outcome related to implant placement; inability to stabilize the implant due to poor quality of bone; implant failure and need for removal; discomfort in function and/or lack of satisfaction with the restoration for other reasons.
- 2) Protection against risks: All efforts will be made to minimize risks to all and every participant: only sites with healthy or almost healthy bone levels will qualify for the study to avert esthetic concerns, prophylactic antibiotics to prevent post-operative infection will be prescribed, restorative and functional expectations will be discussed and explained.

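### Apical radiolucency is read only in sites that had one at the start, so a new apical lesion in a lesion-free site has no specified study measurement

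*Combined protocol and SAP*

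**What the plan says.** Study Subjects lists the reasons for extraction and accepts teeth "with or without radiographic periapical lesion up to 5 mm in diameter". Both kinds of site are therefore expected. The expected share of each is not stated.

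Research Procedures item 4 covers the apex: "The diameter of the apical radiolucency, when initially present, will be monitored". The sentence is broken in the available text, but the condition is clear, and so are the times: the diameter "will be assessed immediately after surgery at 6 months and at 12-18 months".

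Research Procedures item 3 covers interproximal bone: "The mesial and distal crestal bone level will be measured using the MIPACS software". Vertical and horizontal changes of any mesial or distal defect "will be measured from radiographs taken at the time of completion of surgery, at 6 months and 12-18 months". Item 3 carries no subgroup restriction, and it adds: "Dose and frequency of x-rays in the study are standard of care for any implant patient in CDM".

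Potential Risks lists "Initial infection, pain or esthetically adverse outcome related to implant placement" as well as implant failure. No procedure for recording either is given. Under Study Procedures, the permanent restoration is advised at 6 months "if the implant is deemed to be successful", with the criteria given by citation only.

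**The concern.** Take a patient with no periapical lesion before extraction whose 6-month film shows a radiolucency at the implant apex. Item 4 does not apply, because nothing was there at the start. Item 3 applies, but it asks only for the crest and the mesial and distal defects. The film exists, yet no planned data field receives the finding.

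The reading rule is thus one-sided. It can show lesions that resolve, persist or enlarge, but not lesions that appear. At stake is complete reporting of one possible complication in both arms, in a trial that compares two surgical approaches and deliberately enrols sockets with and without prior apical pathology. If the final report is silent on new apical lesions, a reader cannot tell whether none occurred or none were looked for.

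**Working it through.** The plan gives no figure on this point to reproduce. The check is a comparison of the text, followed by a calculation of scale.

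**1. Coverage of the apex**

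| Source | Who | What is read | New apical lesion recorded? |
|---|---|---|---|
| Item 4 | Sites with a radiolucency initially | Its diameter | No |
| Item 3 | No subgroup limit | Mesial and distal crest; mesial and distal defects | No |
| Items 1 and 2a-2f | All | Soft-tissue distance, socket defect dimensions, tissue thickness, pocket depth, ridge dimension, impressions | No |
| 6-month success judgement (Study Procedures) | All | Criteria by citation; no apical reading stated | Not specified |

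No row gives a study measurement of a new apical lesion in a site that began without one.

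**2. Are the films there?** Items 3 and 4 use the same three times. That films are taken in every patient is an inference from the unrestricted wording of item 3 and its standard-of-care statement. That the films show the apex is not stated.

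**3. Sites at risk.** Only a site without a lesion can develop a new one. Planned enrolment is 40 (Power Calculations and Statistical Analysis). Assume that 50-80% are lesion-free; this range is an assumption and has no source in the documents.

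- 0.50 × 40 = 20 sites
- 0.80 × 40 = 32 sites

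**4. What a full reading could support.** With n sites read and no new lesion seen, the one-sided 95% upper bound on the risk is 1 − 0.05^(1/n).

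- n = 20: 1 − 0.05^(1/20) = 0.139, or 13.9%
- n = 32: 1 − 0.05^(1/32) = 0.089, or 8.9%

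These are best cases with every site read. The plan inflates 2 × 17 = 34 to 40, which allows for (40 − 34)/40 = 15% loss. At that loss, 0.85 × 20 = 17 and 0.85 × 32 ≈ 27 sites remain, with bounds of 16.2% and 10.5%.

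**5. By arm.** With the at-risk sites split evenly, there are 10 to 16 per arm.

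- n = 10: 1 − 0.05^(1/10) = 0.259, or about 26%
- n = 16: 1 − 0.05^(1/16) = 0.171, or about 17%

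Bounds this wide allow a description of each arm, not a test between them.

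**6. Might there be anything to see?** Assume 20 at-risk sites and a new-lesion risk of 2%, 5% or 10% (also assumptions). The chance of at least one new lesion, 1 − (1 − p)^20, is 33%, 64% or 88%. As written, none of these would have a planned reading.

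**The case against.** The strongest reply is that item 4 does its own job correctly. It follows the size of a lesion that exists, and for that purpose sites with a lesion are the right set. Apical radiolucency is neither a primary nor a secondary outcome, so no planned result depends on it. This stands, and it keeps the point small.

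A reader might infer three stronger things that the documents do not support.

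- *That a rate of apical lesions by arm will be reported on the wrong denominator.* The plan contains no such rate.
- *That the reading rule guarantees a favourable apical result.* It does not: persisting and enlarging lesions are unfavourable and would be recorded. Only newly appearing lesions go unrecorded.
- *That reading all 40 patients would bound the risk of a new lesion at 7.2%* (1 − 0.05^(1/40)). That figure counts sites with a baseline lesion as at risk of a new one. Under the 50-80% assumption the at-risk number is 20 to 32.

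Two further replies have partial force. A new lesion might be noticed in routine care or in the 6-month success judgement, whose cited criteria are not reproduced in the protocol. So the supportable statement is that no study measurement is specified, not that a lesion would go unseen. Also, the named risk is initial infection, addressed by antibiotics and followed by early healing visits. A radiolucency first seen at 6 months or later is not shown to be that same event, so the case here does not rest on that link.

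**Conclusion.** The point holds as a small, cheaply repaired gap. Item 4 limits the apical reading to lesions present at the start, lesion-free sites are eligible, and nothing else in the plan reads the apex. The trial can therefore describe what happens to existing lesions but cannot report new ones. The named outcomes, the main analysis and the sample size are unaffected.

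On the assumed lesion-free share, the repair replaces no estimate with an upper bound of 8.9% to 13.9% if every at-risk site is read and none shows a new lesion. Any comparison between arms stays descriptive. The conclusion about the text needs no assumption. The size rests on the 50-80% share, and the low cost rests on films being taken in every patient and showing the apex.

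**What to change.** Reword item 4 along these lines: *For every patient, record lesion status before extraction. On the radiographs scheduled at the end of surgery, at 6 months and at 12-18 months, record apical radiolucency as present, absent or not assessable, with its diameter if present.* Pre-extraction status is needed to separate a new lesion from a residual one, since the first scheduled film comes after surgery.

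Add one sentence on reporting, with a separate denominator for each question:

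- new lesions, by arm, among sites without a lesion before extraction;
- resolving, persisting or enlarging lesions, by arm, among sites with one.

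State that both are descriptive, and give the number of films not assessable in each arm.

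The cost is a little extra reading time on films already scheduled. No visit is added, and no exposure is added, provided that films which miss the apex are counted as not assessable rather than repeated. If many miss it, the yield falls accordingly.
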